# **3. PARTICIPANT SELECTION**

## **3.1 Screening, Recruitment, and Consenting**

The investigators will recruit participants from within Boston Medical Center on the inpatient setting. It will be standard for COVID-19 positive patients to be screened to determine if they may be eligible for any available clinical trials. A screening consent is not obtained, as the pre-screening review is conducted prior to contacting the patient to discuss the trial. At that time no data will be collected by the study team. The medical records are reviewed to determine if a patient may or may not be potentially eligible for a clinical trial.

If the patient is potentially eligible, the inpatient nurse, treating physician or trial representative will inform the patient or the patient's legally authorized representative (LAR) of the availability of a clinical trial. No research procedures are performed until after written consent is obtained.

If the patient agrees to discuss and receive information about the study, a copy of the IRB-approved Informed Consent Form will be provided to the patient by a member of the patient's clinical care team to avoid using additional personal protective equipment (PPE). In the event the

patient is too ill to make medical decisions, the patient's LAR will be asked to review the informed consent form, which may be sent electronically.

The inpatient provider will contact the research nurse and provide the phone number of the patient or the LAR. The research nurse and/or investigator will call the patient or the LAR and will remotely conduct the consent discussion, reviewing all elements of consent and emphasizing the voluntary nature of research participation. Additional family members or friends may join the call at the subject's request. Once all questions have been asked and answered to the patient's/LAR's satisfaction, the research nurse will offer to end the call so the patient/LAR can be given the opportunity to review the consent form and discuss with family members (remotely) and/or other physicians. The patient/LAR will have as long to decide as possible within the confines of the clinical urgency. Once the patient/LAR is satisfied that all questions have been answered, if he/she wishes to participate, he/she will contact the research nurse or the research nurse will reach out to the patient/LAR again if requested by the patient/LAR. The study team will have arranged for a witness to join the telephone call at this point, and consent will be obtained remotely, with the patient or LAR directing the witness to sign on their behalf. The informed consent will also be documented in the medical record.

The study team member conducting the consent discussion and the witness will both sign and date the consent form external to the patient's room. The signed consent form will be filed in the research records. The patient will keep the unsigned copy.

Potential participants who are non-English speaking will be consented using the Short Form (if IRB approved). A hospital interpreter, or an interpreter on the phone line, will be used throughout the consent process and throughout their participation in the study. The interpreter will sign as an impartial witness.

Documentation that informed consent occurred prior to the subject's entry into the study and the informed consent process will be recorded in the subject's source documents.

### **3.2 Inclusion Criteria (applicable for patients enrolled for treatment or data collection)**

- Age 18 years or older
- Confirmed COVID-19 infection
- Evidence of cytokine storm defined as:
  - Peak ferritin > 10,000 ng/mL OR
  - Peak ferritin > 500 ng/mL and one or more of the following at any time during hospital admission:
    - Lactate dehydrogenase > 500 U/L, d-dimer > 1000 ng/mL, C-reactive protein > 100 mg/L, or WBC > 15 k/uL
- Cohort 1: Intubated status as a result of COVID infection-associated respiratory illness
- Cohort 2 (if activated): Evidence of progressive respiratory failure (requiring >4 L/min of supplemental oxygen to maintain SaO2 greater than 92%) without intubation

### **3.3 Exclusion Criteria**

- Pregnancy or breastfeeding
- History of severe hypersensitivity to etoposide products
- Absolute neutrophil count (ANC) < 1000 cells/mm^3
- Platelet count <50,000/mm^3
- Bilirubin > 3.0 mg/dL
- Aspartate OR alanine aminotransferase > 5.0 x ULN
- Creatinine Clearance < 15 mL/min (calculated by Cockcroft and Gault formula)
- Requiring continuous renal replacement therapy
- Requiring > 1 vasopressor medications
- Requiring extracorporeal membrane oxygenation (ECMO)
- Other active, life-threatening infections
- Anti-cytokine treatment (including anakinra or IL6 antibodies eg tocilizumab, sarilumab) administration within three half-lives of the medication used
- Hydroxychloroquine, colchicine, azithromycin, doxycycline—if administered for COVID infection—must be discontinued for at least 24 hrs prior to randomization.
- Has a history or current evidence of any condition, therapy or laboratory abnormality that might confound the results of the study, interfere with subject participation, or is not in the best interest of the patient to participate, in the opinion of the investigator.
- Inability to consent and no legally authorized representative
- Poorly controlled HIV infection (CD4 count <100 cells/mm^3)

## **4. INVESTIGATIONAL PLAN**

### **4.1 Overall Design**

Open-label, randomized Phase II study of etoposide administered intravenously at a dose of 150 mg/m^2 once daily on Days 1 and 4 for a total of two doses to inpatient patients with moderate and severe COVID-19 who have consented to treatment on this clinical trial. Dose reductions will be performed as outlined in Section 5.

This study includes a screening period, a treatment period, and a follow-up period for adverse events that will include the remainder of hospitalization, with additional assessments at days 30 and 60 as outlined in the study calendar (Section 6). After obtaining informed consent, the patients randomized to etoposide will begin treatment with the study drug. Subjects randomized to control will receive standard of care treatment. No placebo will be used. Subjects will be monitored for adverse events and to evaluate study outcomes. Patients removed from the study due to any unacceptable adverse events will also be followed until time of death or hospital discharge.

For patients randomized to standard of care, day 1 will be considered day of randomization. These patients will be followed to record the outcome of all primary and secondary objectives until time of death or hospital discharge, whichever occurs earlier.

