## **2.5 Secondary Objectives**

- Overall Survival at 30 days is a key secondary endpoint.
- Improvement in inflammatory markers associated with cytokine storm (Ferritin, C-Reactive Protein (CRP), d-dimer, white blood cell count)
- Cumulative incidence of grade 3 and 4 adverse events during hospitalization
- Cumulative incidence of serious adverse events during hospitalization
- Duration of hospitalization
- Duration of ventilation
- Ventilator free days (reintubations or death within 28 days will result in zero ascribed time off ventilator prior to reintubation)
- Improvement in oxygenation or paO2/FIO2 ratio

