## 6. STUDY PROCEDURES & CALENDAR

REQUIRED STUDIES	Screening	Day 1, Day 4 and Day 7 Σ#	Prior to discharge	Day 30*
PHYSICAL				
History & Physical Exam	X	X	X	X
Height, Weight, Body Mass Index, and Body Surface Area	X			
Vital Signs	X	X	X	X
Toxicity Notation	X	X	X	X
Respiratory Status on 8 point scale ^	X	X	X	X
HISTORY				
Concomitant medicines (including COVID therapies, ie hydroxychloroquine, tocilizumab, anakinra) with date of initiation	X			
Smoking status	X			
Comorbidities	X			
Symptoms, including date of symptom onset	X			
LABORATORY				
Beta HCG (for women of childbearing potential)	X			
CBC with Differential +	X	X	X	X
Comprehensive metabolic panel +	X	X	X	X
Lactate Dehydrogenase	X	X	X	X
D-dimer	X	X	X	X
Ferritin	X	X	X	X
C-reactive protein	X	X	X	X
PaO 2 /FIO 2 (P/F) ratio (cohort 2 only)	X	X	X	X
INR (if on warfarin) Ω	X			
ADDITIONAL TESTING				
Electrocardiogram (ECG)	X			

# For subjects randomized to treatment, the data for Day 1 and Day 4 will be collected prior to the etoposide dose (within 24 hours).

\*Information to be obtained as feasible, if patient has been discharged attempts will be made to obtain the information from the patient's primary care provider. If such results are not available, participant will be contacted by the research nurse to assess toxicities.

^ Mortality assessment (included on the 8 point scale) will also be recorded at Day 14 and 60, in addition to Day 30 mentioned above

+ CBC and comprehensive metabolic panel will be measured at least twice weekly during hospitalization. These tests will also be obtained pre-dose 8, 11, 18, and 25 for those patients who require additional etoposide dosing as described above (Section 4.3 and 5.3)

Ω INR to be repeated at least twice weekly for patients on warfarin

Σ Day 1 of treatment for patients randomized to standard of care (SOC) will be considered the day of randomization

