## 7.2 Statistical Analysis

Tabulations overall, and by treatment group, will be produced for appropriate demographic, baseline, efficacy, and safety parameters, with number and percentages reported for categorical variables and the mean, median, standard deviation, and range for continuous variables. All analyses will be performed at an  $\alpha=0.05$  level using SAS v.4.

Efficacy analyses will be performed in an intention-to-treat (ITT) population consisting of all patients randomized. The difference in ordinal scale improvement rates between treatment arms will be calculated with a 95% confidence interval and formally compared using Fisher's Exact Test. For secondary analysis of the primary endpoint, logistic models individually adjusted for age, diabetes, chronic lung disease/moderate or severe asthma, immunocompromise, liver disease, heart disease/hypertension, smoking and obesity (BMI  $> 40$ ), residence in long-term care facility, will also be examined with odds ratios and 95% confidence intervals reported.

The analysis of secondary time to event endpoints including survival at 30 days, duration of hospitalization, duration of ventilation and ventilator free days, will be compared between treatment arms based on a log-rank test. The median will be estimated with a 95% CI for each treatment arm using the Kaplan-Meier method. Cox proportional Hazards models adjusted individually for age, diabetes, chronic lung disease/moderate or severe asthma, immunocompromise, liver disease, heart disease/hypertension, smoking and obesity (BMI  $> 40$ ), residence in long-term care facility, will also be examined with odds ratios and 95% confidence intervals reported. Changes in inflammatory markers and in oxygenation or  $\text{paO}_2/\text{FIO}_2$  ratio, based on available recorded measurements, will be compared between treatment arms using a two sample t-test, or a Wilcoxon Rank Sum test, as appropriate. Incidence of grade 3 or 4 AEs and serious AEs will be compared using Fisher's Exact test.

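### Section 4.1 ends control-arm follow-up at death or discharge, contradicting the Day 14, 30 and 60 mortality assessments; if followed, 30-day survival is ascertained differently by arm

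*Combined protocol and SAP*

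**What the plan says.** Section 4.1 (Overall Design) contains three statements on follow-up. The study as a whole has follow-up for the rest of the hospital stay, "with additional assessments at days 30 and 60 as outlined in the study calendar". For one subgroup it says: "Patients removed from the study due to any unacceptable adverse events will also be followed until time of death or hospital discharge". Standard-of-care patients are "followed to record the outcome of all primary and secondary objectives until time of death or hospital discharge, whichever occurs earlier".

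Other sections ask for information after discharge and do not limit it by arm:

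- Section 2.5: "Overall Survival at 30 days is a key secondary endpoint".
- Section 6, calendar footnote: "Mortality assessment (included on the 8 point scale) will also be recorded at Day 14 and 60, in addition to Day 30 mentioned above".
- Section 6, Day 30 footnote: "if patient has been discharged attempts will be made to obtain the information from" the primary care provider, with a research-nurse contact about toxicities as the fallback.
- Section 6, footnote bringing controls into the calendar: "Day 1 of treatment for patients randomized to standard of care (SOC) will be considered the day of randomization".
- Section 8.2: the rules for ventilator-free days and days of hospitalization depend on readmission, reintubation and death through Day 28.

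Section 7.2 covers "The analysis of secondary time to event endpoints including survival at 30 days, duration of hospitalization, duration of ventilation and ventilator free days" with a log-rank comparison and Kaplan-Meier estimates. It does not say how a patient discharged before Day 30 enters the survival analysis.

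**The concern.** A control discharged on, say, Day 12 has no recorded 30-day survival under the control-specific sentence in Section 4.1, but should have one under the calendar. The protocol does not say which text prevails. The sentence that singles out controls is the more specific, so staff could reasonably apply it. No matching sentence ends follow-up at discharge for etoposide patients in general; only those removed for unacceptable adverse events share the limit.

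At stake is the comparability of the key secondary endpoint. Discharge is not random with respect to survival: those who leave hospital are those who have recovered. Censoring them in one arm only removes good-prognosis patients from that arm's risk set. Treating them as alive in one arm only misses deaths that would be counted in the other. The trial is open-label, so blinding gives no protection against follow-up that differs by arm. The same sentence also cuts off the 28-day data required by Section 8.2 and, for controls discharged before Day 14, any later change in status before the primary assessment.

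**Working it through.** **The text.** The contradiction needs no arithmetic. For a control discharged alive before Day 30:

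| Source | Is Day 30 vital status recorded? |
|---|---|
| 4.1, control sentence | No, follow-up has ended |
| 4.1, study-wide sentence | Yes, Days 30 and 60 |
| 6, calendar | Yes, Days 14, 30 and 60 |
| 2.5, key secondary endpoint | Needed |
| 8.2, 28-day rules | Needed to Day 28 |

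Controls still in hospital at the assessment day are unaffected.

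**Weight of one patient.** With 24 etoposide and 8 control patients per cohort (Section 2.3), one control with unknown or wrong status is 1/8 = 12.5 points of that arm; one etoposide patient is 1/24 = 4.2 points.

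**Size of the bias if the control sentence is followed.** The plan gives no figure to reproduce and no hazards, so everything below is assumed. The arms are identical, with no true effect. The in-hospital death hazard is *ld* per day from Day 0. Discharge has hazard *lr* per day after a minimum stay of *d* days. The death hazard after discharge is *lp*. Etoposide patients are observed to Day 30.

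With *lp* = 0:

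- True 30-day survival = 1 − {1 − e^(−ld·d) + e^(−ld·d) · [ld/(ld+lr)] · [1 − e^(−(ld+lr)(30−d))]}.
- Kaplan-Meier survival in controls censored at discharge tends to e^(−30·ld), the survival expected if nobody ever left hospital.

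Worked case, *ld* = 0.02, *lr* = 0.03, *d* = 7: e^(−0.14) = 0.869, and 0.4 × (1 − e^(−1.15)) = 0.273. Deaths are 0.131 + 0.869 × 0.273 = 0.368, so true survival is 0.632. The censored estimate is e^(−0.6) = 0.549. The gap is 8.3 points.

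Gap in points, with log-rank rejection at 24:8 and two-sided 5% in brackets (15,000 simulations per cell):

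| ld, lr | d = 14 | d = 7 | d = 0 |
|---|---|---|---|
| .02, .03 | 4.0 (6.3%) | 8.3 (7.3%) | 14.0 (10.4%) |
| .03, .03 | 4.8 (5.8%) | 10.1 (7.1%) | 17.6 (11.6%) |
| .02, .05 | 6.1 (6.0%) | 12.2 (7.6%) | 20.0 (13.1%) |
| .03, .06 | 8.3 (6.2%) | 16.8 (8.5%) | 28.2 (15.0%) |

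With equal follow-up, rejection is 4.4% to 5.7%. These inputs imply true 30-day survival of 0.454 to 0.749. The mean number of the 8 controls discharged by Day 30 is 1.6 to 5.0.

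With *lp* = 0.002 to 0.005 per day, over the same pairs and stays:

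- Censoring only controls at discharge leaves a gap of about 3 to 26 points.
- Counting discharged controls as alive overstates control survival by 0.4 to 6 points; rejection is 3.8% to 6.0%.

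**Lower mortality**, which may suit the non-intubated cohort: *ld* = 0.005 to 0.01, *lr* = 0.03 to 0.06, *lp* = 0. The censoring gap is 2.9 to 8.5 points for *d* = 7 and 1.5 to 4.5 points for *d* = 14.

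**The case against.** The best defence is that the calendar shows the intent. Every Day 30 and Day 60 statement is neutral between arms, a footnote brings controls into the calendar, and a contact route for discharged patients already exists. No text gives etoposide patients longer follow-up in so many words. A difference arises only if staff let one sentence override the calendar for controls while still applying the calendar to etoposide patients. This is a fair account of how the sentence probably came about, and if the calendar is followed there is no arm-dependent ascertainment. But likely intent is a reason to correct the sentence; as written it is explicit about controls and nothing ranks it below the calendar.

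The largest figures are also open to challenge. Discharge from Day 1 is implausible for intubated patients, and all hazards are assumed. Both points stand, so the 14- and 7-day minimum stays deserve more weight than the *d* = 0 column. With a 14-day stay the test is near its nominal level. The harm from censoring further requires an analyst to censor controls alone at discharge, which the plan neither prescribes nor rules out.

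Section 4.5 counts the Day 60 survival assessment as study completion, but it does so under criteria for removal from protocol treatment. It is weak evidence for controls, and the contradiction does not rest on it.

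Finally, censoring at the last date known alive can still mean censoring at discharge for a patient who cannot be reached. That is true, but it would then apply by the same rule in both arms.

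**Conclusion.** The contradiction is established on the text alone, within Section 4.1 and between it and Sections 2.5, 6 and 8.2. It should be fixed. The consequence is conditional: none if the calendar is applied to everyone, or if both arms are handled alike; arm-dependent ascertainment of 30-day survival if the control sentence is applied.

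In the second case the direction turns on an unstated analysis choice. Censoring only controls at discharge would most plausibly favour etoposide; counting discharged controls as alive would favour control. The size rests wholly on assumed hazards and stays. It runs from a few points with long stays or low mortality to well over ten points with short stays and high mortality, with modest inflation of the log-rank error rate except when discharge can come very early. The etoposide arm is not wholly exempt, because patients removed for adverse events carry the same discharge limit. The endpoint is secondary, but the plan itself calls it key, and vital status that is not sought at the time may be hard to recover later.

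**What to change.** Replace both discharge-limited sentences in Section 4.1 with:

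*All randomized patients in both arms, including those removed for adverse events, are followed identically regardless of hospital discharge, with vital status at Days 14, 30 and 60 and readmission and reintubation to at least Day 28.*

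Add to Section 7.2:

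*Hospital discharge is not a censoring event for survival; patients not known to have died are censored at the last date known alive.*

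Reporting the number with unknown Day 30 vital status by arm would show whether any imbalance remains.

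The cost is a wording amendment plus a record check or call for discharged patients, including readmission and reintubation to Day 28. This involves at most 8 controls per cohort (about 2 to 5 under the assumptions above) and any etoposide patients removed for adverse events. The Day 30 contact route in Section 6 already provides the mechanism. Sample size and treatment are unchanged.

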## **4.2 Patient cohorts**

This protocol has two patient cohorts, including cohort 1) severe COVID-19 infection and cohort 2) moderate COVID-19 infection (as defined in the inclusion criteria).

Upon protocol activation, cohort 1 will open to accrual. We will randomize and enroll 10 patients and then perform interim safety analysis prior to further enrollment or opening of cohort 2. See Section 7.2 for statistical design and section 9.5 for stopping rules.

Following treatment with two doses of etoposide (Day 1 and Day 4) in the first 10 participants in cohort 1, safety data including adverse events and patient outcomes will be submitted to the COVID Research Committee for review. At that time, the committee will determine whether they feel that enrollment may be expanded to include cohort 2. If necessary, the COVID Research Committee may ask for safety data to be presented after treating the full 32 patients on cohort 1 prior to opening cohort 2. Only after permitted by the COVID Research Committee will 32 patients on cohort 2 be enrolled and treated. The COVID Research committee is not tasked with medical monitoring, pharmacovigilance or applying stopping rules for this study.

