Additional safety analyses will be based on the reported adverse events and other clinical information. Safety analyses will be performed in the all-treated (AT) population, consisting of all patients who took at least one dose of study treatment. The safety and tolerability of Etoposide will be evaluated by means of drug-related AE reports, physical examinations, and laboratory safety evaluations and compared between groups using Fisher's exact test. The first 10 patients allocated to the Etoposide group in the ventilated cohort will be evaluated for safety endpoints prior to initiating enrollment in the non-ventilated group.

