#### **9.4 Interim Analysis**

Interim analysis will occur after 10 patients are enrolled into cohort 1. Safety data including adverse events and patient outcomes will be presented to the medical monitor (and COVID research committee as detailed in section 4.2). If cohort 2 is activated, an interim analysis will also be performed after 10 patients have enrolled in that cohort.

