#### **9.5 Stopping Rules**

Accrual in a cohort will continue after the interim analysis if  $\geq 1$  of the treated patients in that cohort meets the primary endpoint of 2 point improvement in respiratory status on the 8 point scale at day 14. If cohort 1 is stopped, enrollment in cohort 2 (if open) may still continue.

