## **10.2 Data Safety Monitoring**

Toxicity and accrual monitoring will be performed on a routine basis by the study investigators. Subjects will undergo toxicity assessment and laboratory tests according to the study calendar in Section 7. The clinical status and laboratory reports of the study participants will be assessed routinely by the co-investigators throughout the study. The investigators, Medical Monitor and data analyst will remain as broadly informed as possible regarding emerging evidence from related studies as well as from the conduct of this protocol.

In addition, a Medical Monitor has been appointed to provide additional data safety monitoring. The Medical Monitor is a qualified clinician with relevant expertise, but no direct connection with the research, whose primary responsibility is to provide independent safety monitoring in a timely fashion. The PI will submit a report to the Medical Monitor which will include a list of all adverse events and serious adverse events (regardless of relatedness). In addition, any unanticipated problems involving risks to participants or others and participant deaths will be reported to the monitor as soon as possible and within 24 hours. Additional data may be requested by the Medical Monitor, and interim statistical reports may be generated as deemed necessary and appropriate.

The Medical Monitor is expected to provide a formal, unbiased written report evaluating individual and cumulative participant safety data. Although the PI is responsible for assigning causality and expectedness, the medical monitor will comment on whether or not he is in agreement. As an outcome of each review, the Medical Monitor will make a recommendation as to the advisability of proceeding with study intervention, and to continue, modify, or terminate this trial.

Medical Monitor reports will be submitted to the PI following each review which the PI will, in turn, submit to the IRB. The study will not stop enrollment awaiting these reviews, though the Medical Monitor may recommend temporary or permanent cessation of enrollment based on their safety reviews.

Additional monitoring will also be performed by the COVID Research Committee after 10 patients have been randomized in cohort 1. At that time, the committee will determine whether they feel that enrollment may be expanded to include cohort 2, or may request that data be presented again when all patients on cohort 1 have been treated.

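### The cohort 1 safety look refers to Section 9.5 for stopping rules, but 9.5 holds only a minimum-response criterion, and nothing makes continued accrual in that cohort depend on the safety review

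*Combined protocol and SAP*

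**What the plan says.** Section 4.2 sets the look up as a safety step that holds accrual: "We will randomize and enroll 10 patients and then perform interim safety analysis prior to further enrollment or opening of cohort 2". It then gives the references: "See Section 7.2 for statistical design and section 9.5 for stopping rules".

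Section 9.5 opens "Accrual in a cohort will continue after the interim analysis if" and sets its only condition, which is a count of one or more: "treated patients in that cohort meets the primary endpoint of 2 point improvement in respiratory status on the 8 point scale at day 14". It adds that cohort 2, if open, may go on when cohort 1 is stopped. It does not mention deaths, adverse events, the control arm or the Medical Monitor.

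Three other places bear on the decision:

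- Section 4.2 lets cohort 2 open only with the COVID Research Committee's permission, after the Committee has seen safety data. It limits that body's role, however: "The COVID Research committee is not tasked with medical monitoring, pharmacovigilance or applying stopping rules for this study".
- Section 9.4 gives the timing ("Interim analysis will occur after 10 patients are enrolled into cohort 1") and sends the safety data to the Medical Monitor as well as the Committee.
- Under Section 10.2, after each review, "the Medical Monitor will make a recommendation as to the advisability of proceeding with study intervention". The Monitor may recommend ending the trial or halting enrollment, temporarily or permanently. The same section says that enrollment is not held while these reviews are pending.

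**The concern.** A reader who follows the reference from the safety analysis arrives at a rule that uses no safety data. As worded, one responder is enough for accrual in the cohort to continue. The safety review runs separately and ends in a recommendation. No section says who acts on that recommendation in cohort 1, how it combines with 9.5, or who applies 9.5 at all.

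This matters because cohort 1 consists of intubated patients given a cytotoxic drug. The protocol itself discusses weaker pathogen clearance (1.3) and bacterial super-infection (1.4) as possible harms. If the first look showed an excess of deaths or serious events on etoposide, the one stated accrual rule would point to continuing as soon as a single patient had improved. The team would have to work out during the trial whether the Monitor's view takes precedence and whether patients may be enrolled in the meantime.

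**Working it through.** The plan states no operating characteristics for 9.5, so it has no figure of its own to reproduce. The 80% power in 7.1 is not a premise here. The check has a textual part and an arithmetical part.

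**Text.** The sections set side by side:

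| Section | Data used | Consequence for cohort 1 accrual |
|---|---|---|
| 4.2 | Safety data on 10 patients | Accrual waits for the analysis; rules are said to be in 7.2 and 9.5 |
| 7.2 | Safety endpoints in the first 10 on etoposide | None stated; the condition is on opening the non-ventilated cohort, with no criterion |
| 9.4 | Safety data after 10 are enrolled | None stated; gives timing and recipients |
| 9.5 | Day 14 response in treated patients | Accrual continues with one or more responders |
| 10.2 | Individual and cumulative safety | A recommendation; accrual does not wait |

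Two contradictions follow. Section 4.2 holds enrollment for the look, while 10.2 does not hold it for the Monitor's reviews. The trigger is 10 patients enrolled in 4.2 and 9.4, but 7.2 says "The first 10 patients allocated to the Etoposide group in the ventilated cohort will be evaluated for safety endpoints prior to initiating enrollment" (of non-ventilated patients), which means 10 on etoposide.

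**Number treated at the look.** Section 4.3 gives 3:1 allocation in blocks of 4. The first 10 enrolled fill two blocks (6 etoposide, 2 control) plus two places of a third block. Both of those places are etoposide with probability 3/4 × 2/3 = 1/2; otherwise one is. So n = 7 or 8 if the trigger is 10 enrolled, and n = 10 if it is 10 on etoposide. This assumes that everyone assigned etoposide receives it.

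**Probability that the 9.5 condition is met.** With a true response rate p among treated patients, P(at least one responder) = 1 − (1 − p)^n.

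Illustration with assumed rates, 25% responding and 75% dying by day 14:

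- n = 7: 1 − 0.75^7 = 1 − 0.1335 = 86.7%
- n = 8: 1 − 0.75^8 = 1 − 0.1001 = 90.0%
- n = 10: 1 − 0.75^10 = 1 − 0.0563 = 94.4%

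The 25/75 split is not in the documents, so a range of response rates is shown. The control response rate assumed in 7.1 is 30%.

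| True response rate on etoposide | n = 7 | n = 8 | n = 10 |
|---|---|---|---|
| 5% | 30.2% | 33.7% | 40.1% |
| 10% | 52.2% | 57.0% | 65.1% |
| 20% | 79.0% | 83.2% | 89.3% |
| 25% | 86.7% | 90.0% | 94.4% |
| 30% | 91.8% | 94.2% | 97.2% |

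Mortality enters only by limiting p, because death is category 8 on the scale in 8.2 and a patient who has died cannot be a responder. At a response rate of 10%, one third of the assumed control rate, the condition is still met 52% to 65% of the time, whether the other patients are stable or dead. At the extreme, one responder with every other treated patient dead (6 of 7, 7 of 8 or 9 of 10) meets it.

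**The case against.** The strongest reply is that 9.5 is a minimum-activity rule and was never meant to carry safety. Safety belongs to 9.4 and 10.2. The Monitor is independent, hears of deaths within 24 hours, reviews cumulative data and can recommend termination. Reports that recommend changes go to the IRB within 7 days (10.1). Cohort 2 has a binding gate. Leaving a safety stop to an independent monitor's judgment, without a numerical boundary, is a legitimate choice.

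Much of this stands, and it rules out several stronger readings that a reader might infer:

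- *That the trial cannot be stopped for harm.* Section 10.2 provides a route, and 4.2 controls entry to cohort 2.
- *That 9.5 orders accrual to go on whatever the deaths or toxicity.* That is drawn from its silence. Nothing in 9.5 says that it overrides 10.2.
- *That the rule takes no account of death at all.* Death counts as non-response; what is missing is a separate safety condition.
- *That 87% to 94% is the chance that the trial would continue under harm.* It is the chance that the 9.5 condition alone is met, under assumed rates and before any action by the Monitor.

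The reply does not settle how the two tracks meet in cohort 1. Section 4.2 names 9.5, not 10.2, as the place for stopping rules. Section 9.5 is not made subject to the Monitor's review. The Monitor's power is advisory, the Committee is barred from applying stopping rules, and 10.2 contradicts 4.2 on whether accrual waits.

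**Conclusion.** The point holds as a gap and a contradiction in the stated rules for cohort 1 accrual, not as an absence of safety oversight. The section named for stopping rules contains a response criterion only. No text makes continued accrual in cohort 1 conditional on the safety review, and nobody is named to apply 9.5. The textual finding needs no assumptions. Its size is illustrative: with 25% responding and 75% dying, the 9.5 condition would be met with probability 86.7% to 94.4%, depending on whether 7, 8 or 10 treated patients are counted. It should be corrected before the first look, because the rule governs how many further patients are exposed and the correction is small.

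**What to change.** In 9.5, state that the response criterion is necessary but not sufficient: accrual in a cohort continues after the interim only if the criterion is met and the Medical Monitor's written interim safety review also recommends continuing. Name the person or body that applies the rule.

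Specify what that review contains: deaths in both arms, which 4.1 and the Section 6 calendar already capture, and serious adverse events by arm. The second item needs a change to 9.3, which starts adverse event reporting at the first dose of study drug and so gives controls no start point. Collection for controls should run from randomization.

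Reconcile 4.2, 7.2, 9.4, 9.5 and 10.2 on two matters: whether enrollment pauses for this one interim review, and whether the trigger is 10 enrolled or 10 on etoposide. Changing 9.5 and 4.2 alone would leave the 10.2 sentence in conflict with the new rule.

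No safety threshold is proposed here. The sponsor and the Medical Monitor should settle the criterion before the first look. The cost is a few sentences across these sections, confirmation that control-arm events are collected, and possibly a short accrual pause. No new body is needed, since the Monitor already receives the interim safety data and writes reports.
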